4.1.2 Secondary Endpoints

- 1. The incidence of postoperative joint stiffness (defined as ROM≤95 degrees) measured at the 6week (±2 weeks) postoperative surgical visit
- 2. Postoperative NRS pain scores measured on POD 1, POD 2, at 4 weeks, 3 months, and 6 months postoperatively
- 3. Postoperative knee ROM measured at 6 weeks (±2 weeks) postoperatively
- 4. Postoperative KOOS and PainDETECT (neuropathic pain assessment) scores measured at 4 weeks, 3 months, and 6 months postoperatively
- 5. Time to attainment of physical therapy goals (Ambulation 40 feet, independent transfer) measured during inpatient stay
- 6. New diagnoses and postoperative medications (recorded during hospital admission, during followup visits, and from postoperative phone followups and chart reviews)

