3.0 STUDY HYPOTHESES

1. Elevated levels of TNF-alpha in joint fluid of patients with OA is associated with the risk of development of persistent postoperative pain after TKA.

- 2. Persistent pain (defined as NRS≥4 with activity in the operated joint at 6 months postoperatively) occurs in 10% of patients undergoing TKA for OA.
- 3. Joint stiffness (defined as range of motion [ROM] \leq 95 degrees measured at 6 \pm 2 weeks postoperatively) occurs in 7% of patients undergoing TKA for OA.
- 4. Distinct immune signatures (identified via protein analyses, immunohistochemistry, nanostring, RNA-Seq, fluorescence-activated cell sorting (FACS), and/or mass cytometry [CytoF]) are associated with the risk of developing persistent postoperative pain following TKA in OA patients.
- 5. Distinct immune signatures (identified via protein analyses, immunohistochemistry, nanostring, RNA-seq, FACS, and/or CytoF) are associated with the risk of developing joint stiffness following TKA.
- 6. Demographic profile, comorbidities, psychological factors, pain profiles, pre and postoperative stiffness and inflammatory profiles interact to determine attainment of PT goals and functional outcomes following TKA.

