7.0 STATISTICAL ANALYSIS

- Proposed analysis: Firth's penalized likelihood logistic regression
- Interim analysis planned: No
- Alpha level: 0.05
- Beta or power level: 0.8
- Primary outcome variable estimate (mean +/- s.d. for continuous outcome, frequency/percentage for categorical variable): An estimated 10% of TKR patients will develop persistent postoperative pain (defined as NRS pain ≥ 4 with activity in the operated joint at 6 months postoperatively)
- Number of groups being compared: 1
- Effect size or change expected between groups: It is estimated that a one-standard deviation increase (an estimated 2.6 pg/ml [1]) in intraoperative joint fluid TNFalpha level will be associated with 2.49 times the odds of developing persistent postoperative pain.
- Resulting number per group: Estimating an R 2 of 0.3 if TNFalpha were regressed on model covariates (i.e., model covariates would explain 30% of

the variability in TNFalpha level), a total of 150 patients will need to be enrolled to detect an odds ratio of 2.49.

 Total sample size required: To account for 10% postoperative exclusions, we will enroll a total of 165 patients. 179 patients enrolled

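### The plan links the markers to joint stiffness only as ROM ≤95 degrees (about 11 events); a prespecified regression on continuous 6-week ROM, already a listed endpoint, should stand beside it

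*Combined protocol and SAP*

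**What the plan says.** Objectives 1 and 2 (Section 2.0) ask whether joint fluid and plasma marker levels are associated with patients developing pain or stiffness. Hypothesis 5 (Section 3.0) says that immune signatures "are associated with the risk of developing joint stiffness following TKA". Stiffness is ROM of 95 degrees or less at 6 ± 2 weeks in Sections 3.0, 4.1.2 and 6.2, and Hypothesis 3 says it "occurs in 7% of patients undergoing TKA for OA".

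Section 4.1.2 lists, as secondary endpoint 1, "The incidence of postoperative joint stiffness (defined as ROM≤95 degrees) measured at the 6week (±2 weeks) postoperative surgical visit" and, as secondary endpoint 3, "Postoperative knee ROM measured at 6 weeks (±2 weeks) postoperatively". Section 6.3 collects knee flexion and extension in degrees both before and after surgery.

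Section 7.0 gives one method: "Proposed analysis: Firth's penalized likelihood logistic regression". Its event rate, effect size and sample size all concern pain. It states no model, effect size or power for stiffness, and no analysis of ROM.

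**The concern.** A measurement in degrees is cut at 95, so a knee at 96 counts the same as one at 130. With about 7% of knees below the cut, the binary comparison has few events. If it is the only marker–stiffness analysis, a null result for the stiffness half of Objectives 1 and 2, and for the per-marker tests under Hypothesis 5, would say little about moderate associations. The trial would meanwhile hold ROM data that might show them.

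Leaving the outcome scale open has a second cost. Section 6.1 schedules the cytokine assays for after enrolment is complete. Unless ROM and ROM ≤95 are both assigned a role before marker results are set against outcome, the choice between them can be made after seeing the data.

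**Working it through.** **Inputs from the plan.** "Alpha level: 0.05" and "Beta or power level: 0.8"; sidedness is not stated. Pain rate: "An estimated 10% of TKR patients will develop persistent postoperative pain". Odds ratio (OR) 2.49 per SD of joint fluid TNF-alpha, R² of marker on covariates 0.3, N = 150, 10% postoperative exclusions, 179 enrolled (all Section 7.0). Stiffness incidence 7% (Hypothesis 3).

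**Inputs assumed here.** The OR for stiffness: the plan gives none, so 1.5 to 2.49 is shown. Two-sided alpha. Evaluable N = 179 × 0.90 ≈ 161.

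**1. The plan's own figure.** For logistic regression on a continuous covariate (Hsieh), n = (z_α + z_β)² / [p(1−p)(ln OR)²(1−R²)]. With p = 0.10: (1.960 + 0.842)² / (0.09 × 0.832 × 0.7) = 7.85 / 0.0524 = 149.7, so 150. The plan's figure is reproduced, and two-sided alpha is confirmed (one-sided gives 118).

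**2. Stiffness events.** 0.07 × 150 = 10.5; 0.07 × 161 = 11.3; 0.07 × 179 = 12.5.

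**3. Binary power if OR 2.49 carried over.** Power = Φ(√[N p(1−p)(1−R²)] × ln OR − 1.96). At N = 161: √(161 × 0.0651 × 0.7) × 0.912 − 1.96 = 0.51, so 69.5%. At N = 150 it is 66.5%, and at 179 it is 74.1%. Simulated Firth regression with a penalised likelihood-ratio test gives 60%, 64–65% and 67% at N = 150, 161 and 179. The overall range is 60–74%. By the formula, 80% power at 7% incidence needs 207 patients.

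**4. Continuous ROM.** Suppose ROM is linear in the latent variable whose cut at 95 degrees produces the OR. The implied partial correlation is r = ln OR·√0.7 / √[(ln OR)²·0.7 + π²/3], and power ≈ Φ(atanh(r)·√(N−4) − 1.96). At N = 161, beside simulated power for both tests (ranges show repeat runs):

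| OR per SD | r | Linear, formula | Linear, simulated | Firth, simulated |
|---|---|---|---|---|
| 2.49 | 0.39 | >99% | >99% | 64–65% |
| 2.0 | 0.30 | 98% | 97–98% | 43–45% |
| 1.75 | 0.25 | 89% | 90% | 30% |
| 1.5 | 0.18 | 64% | 64–67% | 17–19% |

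With no effect, the simulated rejection rates were 4.5% (Firth) and 3.7% (linear). Power of 95% needs r = tanh[(1.96 + 1.645)/√(N−4)], which is 0.29 at N = 150 and 0.27 at N = 179.

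**5. Where the gain shrinks or reverses.**
- Weaker correlation: with r at 80%, 70%, 60% or 50% of 0.39, linear power at N = 150 is 97%, 92%, 82% or 66%. The last is no better than the binary formula value of 66.5%.
- Measurement error in ROM lowers both tests, because it also misclassifies knees near the cut. With error SD 10 degrees and 7% observed incidence, power is 45% binary and 97% linear at OR 2.49, and 28% and 82% at OR 2.0.
- Effect only below the cut: at OR 2.49, 62–64% binary and 25–28% linear; at OR 2.0, 43% and 19%.

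**6. Multiplicity.** A 30-plex panel plus adiponectin and leptin is 32 markers. At an illustrative 0.05/32, OR 2.49 gives 17% binary and 97% linear.

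**The case against.** Section 7.0 describes the pain analysis. Applying Firth regression to ROM ≤95 is an inference, and nothing in the plan rules out modelling ROM. This stands: a reader might infer that the plan chose a wrong analysis for stiffness, but the documents show only that none is stated.

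The objectives and Hypothesis 5 ask about developing stiffness. A difference between 110 and 130 degrees is not stiffness as defined here. The Introduction points to fibrosis and to arthrofibrotic tissue, plausibly a process confined to the worst knees, and there the linear test loses. The simulation in which it wins builds in a shift across the whole range. This also stands. It argues against putting continuous ROM in place of ROM ≤95, but not against adding it.

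The precision of the 6-week ROM is unknown. Section 6.2 mentions a goniometer only for the operating-room measurements and states no method for the clinic visit. That is a fair caution, but step 5 shows that measurement error alone does not remove the advantage.

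Finally, the Introduction mentions pathways contributing to restricted motion, so ROM is not absent from the rationale. It is absent from the objectives, hypotheses and stated analysis that concern the markers.

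**Conclusion.** The point holds as an omission. The marker–stiffness question is posed only on a cut expected to give about 11 events, while continuous 6-week ROM is a listed endpoint with no stated analysis against the markers. Adding that analysis would raise power substantially if a marker acts along the whole ROM scale.

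A reader might infer that power would simply rise from 64% to over 95%. The documents do not support that as an unconditional claim. OR 2.49 is the plan's assumption for TNF-alpha and pain; its use for stiffness is an assumption made here. Exceeding 95% also requires a partial correlation of at least about 0.29 at N = 150. At OR 1.5 the linear test reaches only 64–67%, still well above 17–19%. Nor can it be said that the binary test would miss most real associations: at the one effect size the plan gives, its power is 60–74%.

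All powers are for one marker at two-sided 0.05 unless stated. They do not describe the cell, tissue and RNA assays that the Introduction assigns to a subset of 30 patients, where 7% is about 2 stiff knees.

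**What to change.** In Section 7.0, before marker results are examined against outcome:

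- State that the Firth model on ROM ≤95 is the test of stiffness as defined, and keep ROM ≤95 for the incidence estimate (Objective 4, Hypothesis 3).
- Beside it, prespecify a linear regression of 6-week ROM in degrees per SD of each marker measured in the full cohort. Adjust for preoperative ROM, which is already collected and which the Introduction names as a risk factor, and for the covariates of the logistic model. The plan does not list those covariates, so name them here.
- Use robust standard errors if ROM is skewed.
- Say that this does not extend to assays planned only in the 30-patient subset.

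The cost is a few sentences and one more regression per marker, with no new visits, data or patients. The added effect is in degrees per SD rather than an odds ratio, and each added test must be counted in any multiplicity control.

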4.2 Study Sites

This study will take place at the main campus of the Hospital for Special Surgery (HSS).

5.0 STUDY POPULATION

5.1 Number of Subjects

179

5.2 Inclusion Criteria

Subjects of either gender will be included if:

- Elective primary unilateral total knee arthroplasty
- OA with radiologic evidence of "severe narrowing" and/or "bone on bone" in the affected joint
- Patients of surgeons who have agreed to participate in the study
- Age > 18 years
- American Society of Anesthesiologists (ASA) physical status 1-3
- Regional anesthesia
- Epidural PCA for postoperative pain
- Adductor canal block for postoperative pain

5.3 Exclusion Criteria

Subjects will be excluded from the study if:

- Contraindication to regional anesthesia, NSAIDs, dexamethasone or acetaminophen
- Use of general anesthesia
- History of >6 weeks of daily opioid use and/or any use of non-prescribed opioids
- Preoperative systemic steroid use in the past 6 months
- Intra-articular steroid injection within one month of scheduled surgery in affected joint
- Non-English speakers
- Pre-existing diagnosis of rheumatic disease, autoimmune disease or immunodeficiency (e.g., rheumatoid arthritis, psoriatic arthritis, inflammatory bowel disease, multiple sclerosis, Type 1 diabetes)
- Peri-articular injections or infusions for postoperative pain
- Diagnosis of crystalline arthropathy
- Diagnosis of osteonecrosis
- Active infection or use of antibiotics
- Pregnant women
- Previous study participants

6.0 PROCEDURES

6.1 Intraoperative Protocol

Anesthesia and Analgesia:

The intraoperative anesthesia regimen will be standardized to include neuraxial anesthesia with an epidural. Patients must receive 4mg dexamethasone for nausea prophylaxis. Propofol, midazolam, up to 100mcg fentanyl and up to 30mg ketorolac can be administered intraoperatively at the discretion of the anesthesiologist. Ketamine and dexmedetomidine will not be administered. Violations of intraoperative anesthesia guidelines will be grounds for exclusion at the discretion of the PI in consultation with the anesthesia provider.

The postoperative pain regimen will include: adductor canal nerve block (local anesthetic with no additives) and the default TKA orderset (postoperative epidural patient controlled analgesia with standard settings, prn oxycodone or hydrocodone 5mg10mg q4h, PO or IV acetaminophen standing dose or prn, and meloxicam). Postoperative pain management regimens will be adjusted by the pain management team as required to achieve adequate analgesia. Chronic pain patients will be maintained on standing and prn pain medications prescribed at the discretion of the treating chronic pain physician. Epidural PCA failure requiring use of IV PCA will be ground for exclusion after enrollment.

Sample Collection:

During hospital admission, baseline (prior to surgical incision), early postoperative (drawn on arrival to PACU), POD 1 (24±2 h), and POD 2 (48±2 h) blood samples will be collected for each enrolled patient from a preexisting arterial line or by venous or arterial puncture if an arterial line is not in place. In the operating room, participating surgeons will draw joint fluid aspirates (up to 5mL) prior to surgical arthrotomy and will collect intraoperative tissue samples that will be sent to pathology for processing.

For all enrolled patients:

Inpatient whole blood samples: maximum 80mL

- · Baseline: 30mL + 1 PAXgene tubes (2.5mL)
- · Early postoperative: 5mL + 1 PAXgene tubes (2.5mL)
- · POD 1 (24 h): 30mL + 1 PAXgene tubes (2.5mL)
- · POD 2 (48 h): 5mL + 1 PAXgene tubes (2.5mL)

Possible 6 week follow up visit whole blood sample: Max 60mL

After samples are collected, aliquots of blood, plasma and joint fluid will be frozen and stored for future analyses. PAXgene tubes will be stored for future RNA analyses. Sample analysis: Once enrollment is complete, joint fluid and plasma samples will be analyzed for TNFalpha and other cytokine and chemokine levels by the CTSC at Cornell using 30plex panels from Mesoscale. Adiponectin and leptin levels will also be assessed using Mesoscale assays. In addition, fresh blood samples will be processed for cellular and molecular analyses of inflammatory and related pathways using methods potentially including FACS and/or CytoF, RNA analyses, and protein analyses (e.g., assessment of Rho associated protein kinase (ROCK) activity) to be conducted at HSS in the lab of [name], the precision medicine core facility at HSS and/or affiliated core facilities at WCMC/RU/MSKCC). In the event that blood work cannot be collected at the 6week visit (±2

[figure not shown]
weeks), blood work may be collected at the 3month postoperative visit. Sample Analyses which may be performed (on deidentified samples) by our coinvestigators, the precision medicine laboratory at HSS, affiliated core facilities at WCMC/RU/MSKCC, and/or outside facilities include: · Blood Cells: After blood is collected, composition of white blood cell differential (PMN, monocyte, lymphocytes) may be documented by flow cytometer and/or CytoF. Samples may then be sorted into granulocytes, PBMC, and platelet poor plasma, and cells viably frozen for future validation of RNAseq data. An aliquot of the PBMCs will be directly assayed for ROCK activation, immune cell subsets and T cell function. Another aliquot will be cultured to assess ROCK activation and T cell function after stimulation by measuring molecules such asIRF4, IRF5, IRF8, IBP/Def6, SWAP70, ROCK1, ROCK2, and signaling molecules involved in responsiveness to activation stimuli. Samples may be then subjected to QPCR, Western blotting, immunofluorescence / immunohistochemical analysis, ELISA, FACS or other laboratory analysis to investigate the expression/function of the signaling components that might be implicated in OA and poor postarthroplasty outcomes. If deemed necessary CD4+ T cell purification will be performed, after which the cells will be either left unstimulated or stimulated.

- · PAX tube (2.5 mL or 0.5 tsp): RNA samples extracted from PaxGene tubes may be analyzed using RNA sequencing technology, RNA microarray, quantitative PCR, RNA nanostring or other appropriate RNA analysis platforms. Unique reads will be mapped to a reference human genome.
- · Blue, green and red top tubes: Plasma will be collected and may be used for measurement of cytokines and other proteins potentially contributing to OA and post-arthroplasty outcomes.

In keeping with the protocols of the AMP studies, intraoperative tissue samples may be collected with special attention to obtaining samples of tissues from standardized anatomic locations including tissue samples of the patella cartilage, distal femur and proximal tibia, and synovium from the suprapatellar pouch.

- Tissue will be processed first in pathology: sample saved in OCT and 2 slides stained with H&E. Slides will be scored according to a modified Scanzello scoring system. Synovial tissue and PBMCs will be processed according the standard operating procedures established by the AMP network. Cellular samples will be analyzed at HSS, and may be shared with the AMP network or other collaborating institutions (in a deidentified manner) for additional specialized technical analytics to explore markers and pathways expressed in tissue and cells, using (but not limited to) those being explored in the AMP network such as RNASeq, ATACSeq, CyTOF, FACS
- Analysis may also include photography of specimens using the Pathology Lab equipment. The resulting photographs will be deidentified before use for research purposes. We may also capture deidentified microscopy images of H&E slides prepared from these samples.

Research specimens will be divided into four aliquots. As discussed with [name], all processing in Pathology will be performed by the Rheumatology Research Assistant under the direct supervision of the pathologist or representative.

• The first aliquot will be frozen and sectioned for staining with hematoxylin and eosin for tissue identification and for any later processing that might require fresh frozen tissue. The frozen tissue block (minimum 0.5 cm in diameter) will be preserved in the cryomold and taken to the [name] lab for storage in the 80degree Celsius freezer.

- The second aliquot will be stored fresh in a tube with RNAlater and will be brought by a research assistant to a research assistant to be used for RNA sequencing and/or nanostring or qPCR. The samples will be frozen and subsequently thawed, and RNA will be extracted using an approved methodology (e.g., the TRIzol Plus RNA purification system (Life Technologies)). RNA will be reverse transcribed and a cDNA library will be generated and sequenced on a HiSeq 2500. Data will be processed by filtering, genome mapping with STAR, and raw read counts will then be processed with edgeR for differential gene expression comparing synovial samples from patients who flared to those who did not flare in 6 weeks of followup.
- The third aliquot will be processed in the HSS pathology laboratory for fixation, paraffin embedding and sectioning, and standard of care hematoxylin and eosin staining.
- · The fourth aliquot will be processed in the [name] and [name] laboratories to isolate live synoviocyte cells.

Specifically, a fragment of synovial lining (~2 cm3†or greater) will be diced into smaller fragments and cells disloged from the matrix by mechanical force and/or enzymatic digestion. The resulting singlecell suspensions will be stained for celltype specific surface markers by FACS and/or CytoF and sorted by flow cytometry. In particular, T and B cell, monocyte and fibroblast populations will be collected. Downstream analyses include various nextgeneration sequencing protocols, which assay for gene expression levels and epigenetic features. The goal of this procedure is to identify cell populations or intracellular pathways found directly within the diseased tissue that associate with other disease parameters.

· From the remaining tissue, HSS pathology will conduct fixation, paraffin embedding, sectioning, and standard of care histopathologic examination.

At least 2 formalin fixed, paraffin embedded tissue blocks will be taken and kept in the pathology department. (Rheumatology research assistant should record Pathology Accession.)

Additional processing of aliquot #1 will include staining for a panel of cytokines known to characterize the presence/recruitment of specific immune cell subsets, particularly Th17 and Th1 cells (IL17, IL21, IFNgamma, and CCL20) as well as the activity state of the ROCK pathway (e.g., by staining for phosphorylated ERM, a well established target of ROCK activity and by staining with newly developed antibodies against phosphorylated ROCK2, IRF4, and IRF8). The expression of these molecules will be further confirmed in the second aliquot after extracting RNA and subjecting the samples to qPCR analysis and/or nanostring. Staining for the expression/activity of these molecules in fresh frozen tissues will only be performed if staining in the formalin fixed, paraffin embedded tissues (aliquot #3) is not successful.

[figure not shown]
Deidentified samples will then be brought to the [name] lab or other collaborating lab/core facility and subjected to immunofluorescence / immunohistochemical analysis to investigate the expression/function of the signaling components that might be implicated in OA and poor postarthroplasty outcomes. In particular these studies may assess the composition of the inflammatory infiltrates, the activation state of distinct cellular subsets, the activity of the ROCK pathway (e.g. by staining for pERM a target of Rock activity), and other pathways associated with inflammation, fibrosis, and oxidative stress.

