2.0 OBJECTIVE(S) OF CLINICAL STUDY

This study is novel in taking a systematic approach to identifying and characterizing persistent pain and joint stiffness following TKA and analyzing activity of inflammatory pathways that may contribute to the development of these complications at a cellular and molecular level. This study has unique potential to fill in gaps in our understanding of how molecular and cellular pathology are associated with demographic factors, psychological factors, and medical comorbidities that contribute to postoperative pain and stiffness.

This study is designed to give us a better understanding of the inflammatory milieu associated with and potentially contributing to the development of persistent pain and/or joint stiffness after TKA. A better understanding of inflammatory contributors and clinical risk factors may allow us to recognize patients at high risk of these complications and may enable targeted interventions to reduce their incidence.

- 1. Determine if there is an association between preoperative joint fluid TNF-alpha, cytokine, chemokine, and adipokine levels and development of persistent postoperative pain and/or joint stiffness after TKA.
- 2. Determine if there is an association between preoperative plasma TNF-alpha, cytokine, chemokine, and adipokine levels and development of persistent postoperative pain and/or joint stiffness after TKA.
- 3. Determine the incidence, characteristics, and kinetics of persistent postoperative pain after TKA.
- 4. Determine the incidence, characteristics, and kinetics of postoperative joint stiffness after TKA.
- 5. Collect and store blood, joint fluid, and joint tissue for exploration of inflammatory signatures (identified by protein analyses, immunohistochemistry, RNA analysis including nanostring and sequencing analysis [RNAseq] and/or cellular analysis including flow cytometry and mass cytometry [cytoF]) associated with and potentially contributing to development of persistent postoperative pain and/or joint stiffness after TKA.
- 6. Collect clinical data for examination of interactions between demographic factors, comorbidities, pre- and post-operative pain, joint stiffness, inflammatory profiles, postoperative attainment of physical therapy (PT) goals, and functional outcomes after TKA.

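### The only stated group contrast for the synovial RNA-seq (edgeR) analysis is flare versus no flare, which this protocol neither defines nor records and which does not match Objective 5 or Hypotheses 4 and 5

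*Combined protocol and SAP*

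**What the plan says.** In Section 6.1 the second tissue aliquot is "to be used for RNA sequencing and/or nanostring or qPCR". If it is sequenced, the reads are mapped and the counts go to edgeR for differential gene expression, "comparing synovial samples from patients who flared to those who did not flare in 6 weeks of followup". The choice of assay is left open, but the contrast is stated without qualification.

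Elsewhere the protocol gives the signature work a different target:

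- Objective 5 (Section 2.0) is to collect and store samples to explore inflammatory signatures, RNAseq among them, "associated with and potentially contributing to development of persistent postoperative pain and/or joint stiffness after TKA".
- Hypothesis 4 (Section 3.0) is that distinct immune signatures, with RNA-Seq in the list of methods, "are associated with the risk of developing persistent postoperative pain following TKA in OA patients".
- Hypothesis 5 says that such signatures "are associated with the risk of developing joint stiffness following TKA".
- Section 6.1 directs the neighbouring tissue staining at "the signaling components that might be implicated in OA and poor postarthroplasty outcomes".

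Section 6.2 defines both outcome groups, and Section 6.3 records each as a yes/no item.

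The Introduction (Section 1.0) adds that 30 enrolled patients will be co-enrolled in the control cohort of a rheumatoid arthritis study named FLARE, and that their blood and tissue will be stored for cell-based, histological and RNA analyses, including RNAseq.

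**The concern.** In a differential-expression analysis the group label determines what is tested. Here the one label given is a term the protocol does not define, and the outcomes that its objectives and hypotheses name are absent from the sentence. An analyst following the text would have to choose the groups later: pain, stiffness, either one, or some 6-week construct. A reader of the results could not then tell a planned contrast from one chosen after the data were seen. What is at stake is the traceability of one exploratory analysis.

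**Working it through.** The check is mainly textual. The protocol gives no sample size, rate or threshold for this analysis, so it has no figure of its own to reproduce.

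**Step 1. Where flare appears.** The word occurs three times in any form: once in the Introduction, as the name of another study, and twice in the edgeR clause of Section 6.1. It does not occur in the objectives (2.0), hypotheses (3.0), endpoints (4.1), outcome definitions (6.2), data items (Synopsis and 6.3) or statistical analysis (7.0).

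**Step 2. Whether a listed item could stand in for it.**

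- Secondary endpoint 6, "New diagnoses and postoperative medications", neither names nor defines a flare.
- Secondary endpoint 1 is "The incidence of postoperative joint stiffness (defined as ROM≤95 degrees) measured at the 6week (±2 weeks) postoperative surgical visit". Its nominal timing agrees with the 6 weeks in the edgeR clause, but it is defined by range of motion and is never called a flare.
- Persistent pain is assessed at 6 months, so a 6-week flare cannot be that outcome. One term therefore cannot cover both outcomes named in Objective 5.
- Section 5.3 excludes patients with a pre-existing diagnosis of rheumatic disease, rheumatoid arthritis included, and the 30 co-enrolled patients serve as controls. Nothing here supplies a flare group by that route.

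**Step 3. Whether another section gives the contrast.** Section 7.0 covers Firth's penalized logistic regression, with its effect size stated for joint fluid TNF-alpha. It gives no RNA-seq grouping, so the Section 6.1 clause is the only one.

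**Step 4. Size of the contrasts that the objectives imply.** The inputs are 179 enrolled (5.1), 30 co-enrolled (1.0), a 10% rate of persistent pain (3.0 and 7.0) and a 7% rate of stiffness (3.0). Expected cases = patients sequenced × rate.

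| Patients sequenced | Persistent pain | Joint stiffness |
|---|---|---|
| All 179 | 179 × 0.10 = 17.9, about 18 | 179 × 0.07 = 12.5, about 13 |
| Only the 30 co-enrolled | 30 × 0.10 = 3.0 | 30 × 0.07 = 2.1, about 2 |

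The text does not settle which row applies. Section 6.1 does not restrict tissue collection to the 30, while the Introduction mentions tissue RNAseq in connection with them. With 30 patients the chance of at most one case is 0.9^30 + 30 × 0.1 × 0.9^29 = 0.18 for pain, and 0.93^30 + 30 × 0.07 × 0.93^29 = 0.37 for stiffness. No size can be computed for a flare group, because no definition or rate is given.

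**Step 5. Whether the primary analysis is touched.** The primary sample size uses a 10% event rate, an odds ratio of 2.49 per SD and R² = 0.3. Taking alpha 0.05 as two-sided (an assumption, as sidedness is not stated) and power 0.8, n = (1.960 + 0.842)² / [0.10 × 0.90 × (ln 2.49)²] = 104.8, and 104.8 / 0.7 = 149.7, which rounds up to the stated 150. Flare does not enter it.

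**The case against.** The best defence is that the sentence describes the FLARE study. The Introduction links tissue RNAseq to the 30 co-enrolled patients, and flare may be defined and recorded under that study's own protocol, which is not among these documents. This stands as a possible explanation. It also means that the contrast cannot be called unusable in general, only that it cannot be run from what this protocol lists. It does not remove the problem: Section 6.1 does not limit the sentence to that study, and if it belongs there, this protocol states no synovial RNA-seq contrast of its own.

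A second defence is that nothing in the aims is contradicted. Objective 5 is to collect and store samples for exploration, Hypotheses 4 and 5 join their methods with and/or, and Section 6.1 does not say that its contrast is the only one permitted. This is largely right. The mismatch is unreconciled, but the clause does not prevent the aims from being met.

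A third is that the intended groups can be recovered from Sections 2.0, 3.0 and 6.2. That is also right, and it limits the harm.

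**Conclusion.** The point holds as a minor inconsistency. The only stated contrast for the synovial RNA-seq analysis uses a grouping that this protocol does not define, list as an endpoint or record, and it does not match the outcomes in Objective 5 and Hypotheses 4 and 5. Neither of its two groups can be filled from the listed data.

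Three stronger readings are tempting, and the documents do not support them.

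- A reader might infer that the clause was carried over by mistake from the FLARE study. The shared word and the co-enrolment make this possible, but no passage says it.
- A reader might infer that Hypotheses 4 and 5 can no longer be tested. They can: the same read counts can be compared on the pain and stiffness groups, and blood RNA and the joint fluid and plasma protein panels are also available.
- A reader might infer that the main result is at risk. The synovial sequencing is exploratory and optional, and the TNF-alpha analysis and its sample size do not depend on it.

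The case counts of about 18 and 13, or about 3 and 2, rest on the protocol's assumed 10% and 7% rates. They also assume usable tissue and outcome data from every patient counted, so they are upper-end expectations at those rates.

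**What to change.** State in Section 6.1 which study the edgeR sentence describes. If it is the FLARE study, keep the sentence and attribute it there. If it is not, replace the flare clause.

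In either case, add this study's own contrast. For example: exploratory differential expression will compare synovial samples from patients with and without persistent pain (activity NRS of 4 or more in the operated joint at 6 months), and from patients with and without joint stiffness (ROM of 95 degrees or less at the 6±2-week visit), both as defined in Section 6.2. Say also whether tissue from all patients or only from the 30 co-enrolled will be sequenced.

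The cost is one or two sentences. No visit, sample or data item is added, because both outcomes are already collected. There are two downsides: the pain contrast must wait for the 6-month data, and case numbers are small, very small if only the 30 are sequenced. The results should therefore be labelled exploratory.
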